#### 3.3.2. Benefit Assessment

- All participants will undergo a thorough medical assessment during the study. Participants will have study clinic visits for the evaluation of their disease symptoms. During these visits, participants will have spirometry, ECG, vital signs monitoring, and physical examinations.
- Participants may benefit from the knowledge that they are contributing to the process of developing a new treatment in an area of unmet need, even if not directly beneficial for them.

#### 3.3.3. Overall Benefit:Risk Conclusion

Danirixin has demonstrated potent antagonism of CXCR2 activity both *in vitro* and *in vivo* in preclinical and clinical studies. Its potency and duration of action supports its potential use as an oral, anti inflammatory agent in the treatment of COPD with anticipated potential for bringing benefit to a serious condition that affects the lives of millions and contributes to significant morbidity and mortality. To date no significant risks have been identified for danirixin from toxicology data or completed and ongoing clinical studies. While the potential for AEs related to testicular effects or impaired neutrophil response cannot be dismissed, no such effects have been observed in healthy subjects, or in subjects with COPD or influenza. Data regarding host response outcomes in COPD and influenza are limited, but no increase in infections have been observed to date.

Taking into account the measures taken to minimize risks to participants in this study, the potential risks identified in association with danirixin are justified by the anticipated benefits that may be afforded to participants with COPD.

Objectives	Endpoints
Primary	
• To assess the change from baseline in NETs formation in participants with COPD following 14 days treatment with danirixin HBr 35mg twice daily	• Reduction in sputum NETs (quantified by Histone-elastase complexes)
Secondary	
• To assess the change from baseline in NETs formation in participants with COPD following 14 days treatment with danirixin HBr 35mg twice daily	
 
Reduction in sputum NETS (quantified by Deoxyribonucleic acid [DNA]-elastase complexes)
 
Reduction in sputum NET area quantification by microscopy
 

• To further characterize the safety of danirixin HBr 35mg twice daily compared with placebo in	

Adverse events

Vital Signs

ECG

# 4. OBJECTIVES AND ENDPOINTS

	Objectives		Endpoints
	participants with COPD	•	Spirometry Clinical Laboratory Assessments (hematology, clinical chemistry, urinalysis)
•	To assess the effects of danirixin HBr 35mg twice daily on NETosis- associated biomarkers in sputum and	•	Change from baseline in sputum resistin levels
	peripheral blood	•	Change from baseline in the ratio of sputum NETs to sputum neutrophils
		•	Change from baseline in sputum elastase activity
		•	Change from baseline in peripheral blood neutrophil NET formation (DNA release, microscopy)
•	Characterise the population pharmacokinetic (PK) profile of approximately 14 days of dosing of danirixin HBr 35mg twice daily in participants with COPD	•	Model specific PK parameters of danirixin (e.g., oral clearance, oral steady- state volume of distribution).
Ex	ploratory		
•	To explore the relationships between NETs formation and lung microbiome composition	•	Characterize sputum microbiome composition and diversity
•	To explore volatile organic compound (VOC) profile in participants with COPD	•	Characterize relationship between lung microbiome and exhaled volatile organic compounds (VOCs) in stable COPD To explore variability of exhaled VOCs
•	To explore the effects of danirixin HBr 35mg twice daily on neutrophil activity and exploratory biomarkers	•	Changes from baseline in ex-vivo neutrophil phagocytosis of bacteria by flow cytometry Changes in exploratory urine, sputum and blood biomarkers (e.g. plasma fibrinogen, serum C-reactive protein, serum IL-8 or sputum mucin)
•	To explore the effects of an App on adherence to treatment with danirixin or placebo	•	Characterize treatment adherence in relation to monitoring via App and explore relationship to PK parameters

# 5. STUDY DESIGN

## 5.1. Overall Design

[figure not shown]
A study schematic is shown in Figure 1. This is a parallel group study. Following screening, participants will be randomized (3:1) to receive danirixin 35 mg or placebo. Study treatment will be administered twice daily for 2 weeks.

Based on the observed variability at an interim analysis, additional subjects may be enrolled to improve the statistical properties of the end of study decision criteria (i.e., the probability of a positive outcome). Outputs containing unblinded treatment assignments will be created for this interim analysis will only be made available to a limited number of GSK staff. Full details will be included in the study data dissemination plan. No Independent Data Monitoring Committee (IDMC) will be utilized for this study.

While the study is being conducted, core members of the study team will be unblinded (with the exception of those study team members who will directly interact with study sites, e.g. Operations and Science Leader and Data Quality Leader). There will be ongoing review of safety data and clinical outcomes. Only the study statistician will have access to individual participant treatment assignments, other core team members will review aggregate summaries by study treatments. A study charter will specify which team members will have access to unblinded data while the study is ongoing and the data to be included in the data reviews.

The danirixin safety review team will perform ongoing safety review and will meet at least once while the study is ongoing and as needed based on emerging data to review available safety information.

• Follow up phone-call to occur within 7 days of last dose of study medication

## 5.2. Number of Participants

Approximately 50 participants will be screened to obtain approximately 24 subjects who are randomized and also complete the primary endpoint assessment at Day 14. It is anticipated that less than 10% of participants will drop out of the study given the short duration of treatment.

A maximum of 32 participants will be randomized such that approximately 24 evaluable participants complete the study. An evaluable participant is one that completes all assessments related to the primary endpoint at visits 0 - 4 (see Section 10.1 for further details).

If participants prematurely discontinue the study, additional replacement participants may be recruited and assigned to the same treatment sequence at the discretion of the Sponsor in consultation with the investigator.

## 5.3. Participant and Study Completion

A participant is considered to have completed the study if he/she has completed all phases of the study including the last visit.

The end of the study is defined as the date of the last visit of the last participant in the study in the trial.

## 5.4. Scientific Rationale for Study Design

This study is designed as a mechanistic study to evaluate the effect of danixirin in reducing NET formation. NET formation has been studied across several human studies, however consensus has not been reached on identification of NETs, which relies upon detection of DNA. Presence of bacterial DNA can confound results from sputum, therefore detection of histone elastase complexes is increasingly recognised as a specific and robust assay for detection of NETosis, and is used as the primary endpoint. The duration of treatment, 2 weeks, is adequate to see treatment effect given that neutrophil lifespan is 1-2 days.

## 5.5. Dose Justification

One dose of danirixin is proposed for this study, 35mg twice daily. This dose was selected based on integrating information on:

- Dose-exposure-biomarker response using inhibition of *ex vivo* CXCL1-induced CD11b expression on peripheral blood neutrophils over the dose range of 0-400mg free base in healthy volunteers
- Evidence of reduced respiratory symptoms in mild to moderate COPD participants in the Phase IIa study (200163)
- Relative bioavailability study comparing danirixin free base vs HBr

#### CONFIDENTIAL

Analysis of the percent inhibition achieved across the pooled data from studies in healthy volunteers indicated that the maximum possible inhibition of CXCL1-induced CD11b activated neutrophil expression had been achieved following oral administration of danirixin at a nominal dose of 200 mg BID.

In Phase IIa COPD study (200163), a dose of danirixin (free base) 75 mg BID resulted in a reduction in respiratory symptoms compared to placebo.

The danirixin formulation to be used in this study (207551) will be a hydrobromide salt tablet. The hydrobromide tablet has approximately twice the exposure of the free base tablet in healthy elderly participants (GSK Study No. 201037). Based on the anticipated higher exposure from the hydrobromide tablet, the 35 mg twice daily dose was selected for this study to maximize the potential to see any impact on NET formation.

# 6. STUDY POPULATION

Prospective approval of protocol deviations to recruitment and enrollment criteria, also known as protocol waivers or exemptions, is not permitted.

#### 6.1. Inclusion Criteria

Participants are eligible to be included in the study only if all of the following criteria apply:

#### Age

1. Participant must be 50 to 75 years of age inclusive, at the time of signing the informed consent.

#### Type of Participant and Disease Characteristics

- Diagnosis of COPD with mild to moderate airflow obstruction (post-bronchodilator FEV1/ Forced Vital Capacity (FVC) ratio <0.7 and FEV1% predicted (pred) ≥40% at screening) based on the Quanjer reference equations, with spirometry conducted according to American Thoracic Society (ATS)/European Respiratory Society (ERS) current guidelines.
- 3. Elevated sputum neutrophil extracellular traps based on screening assay for histoneelastase complexes of >0.5 units/ml sputum. Two further screening samples can be submitted for analysis within 30day screening period if previous samples do not pass criteria.
- 4. Able to produce at least 1ml of sputum sample at the screening visit with nebulised saline induction
- Current smokers and former smokers with a cigarette smoking history of ≥10 pack years (1 pack year = 20 cigarettes smoked per day for 1 year or equivalent). Former smokers are defined as those who have stopped smoking for at least 6 months prior to Visit 1.

#### Weight

6. Body weight  $\geq$ 45 kg

#### Sex

7. Male or female

#### a. Male participants:

A male participant must agree to use contraception as detailed in Appendix 5 of this protocol during the treatment period and for at least [60 hours, corresponding to approximately 6 half-lives (which is the time needed to eliminate any teratogenic treatments after the last dose of study treatment and refrain from donating sperm during this period.

#### b. Female participants:

A female participant is eligible to participate if she is not pregnant (see Appendix 5), not breastfeeding, and at least one of the following conditions applies:

(i) Not a woman of childbearing potential (WOCBP) as defined in Appendix 5

OR

(ii) A WOCBP who agrees to follow the contraceptive guidance in Appendix 5 during the treatment period and for at least 60 hours after the last dose of study treatment.

#### **Informed Consent**

8. Capable of giving signed informed consent as described in Appendix 3 which includes compliance with the requirements and restrictions listed in the informed consent form (ICF) and in this protocol.

#### 6.2. Exclusion Criteria

Participants are excluded from the study if any of the following criteria apply:

#### **Medical Conditions**

- 1. Primary clinical diagnoses of any of the following relevant lung diseases; asthma, sarcoidosis, tuberculosis, pulmonary fibrosis, severe bronchiectasis or lung cancer
- 2. Known alpha-1-antitrypsin deficiency
- 3. Pulse oximetry <88% at rest at screening. Participants should be tested while breathing room air.
- 4. Participants on long term oxygen therapy (defined as >15 hours/day of oxygen use)
- 5. Unstable co-morbidities (eg cardiovascular disease, active malignancy) which in the opinion of the Investigator would make the participant unsuitable to be enrolled in the study. This includes any abnormality identified on screening bloods or screening ECG which in the opinion of the Investigator would make the participant unsuitable for the study.

- 6. History of sensitivity to any of the study medications, or components thereof or a history of drug or other allergy that, in the opinion of the investigator of GSK medical monitor, contraindicates their participation.
- 7. Current or chronic history of liver disease, or know hepatic or biliary abnormalities (with the exception of Gilbert's syndrome or asymptomatic gallstones).
- 8. Participants with a known or suspected history of alcohol or drug abuse within the last 2 years

#### **Prior/Concomitant Therapy**

- 9. Antibiotic use concurrently or within 28 days preceding the screening visit, including current or planned chronic use of macrolide antibiotics during the study period for the prevention of COPD exacerbations. Examples of chronic use include daily or two-three times per week for at least 3 months
- 10. Systemic immunosuppressive medication, including current oral corticosteroids at a dose >5mg, concurrently or within 28 days preceding the screening visit.
- 11. Oral or injectable Cytochrome P450 (CYP) 3A4 or Breast Cancer Resistance Protein (BCRP) substrates with narrow therapeutic index (CYP3A4 substrates include, but are not limited to, alfentanil, cyclosporine, dihydroergotamine, ergotamine, fentanyl, pimozide, quinidine, sirolimus, tacrolimus, and theophylline; BCRP substrates include: Methotrexate, mitoxantrone, imatinib, irinotecan, lapatinib, rosuvastatin, sulfasalazine, topotecan.
- 12. Current use of phosphodiesterase-4 inhibitors: Roflumilast, Crisaborole and Apremilast
- 13. Current use of Raloxifene
- 14. Current use of low molecular weight heparin

#### **Prior/Concurrent Clinical Study Experience**

- 15. The participant has participated in a clinical trial and has received an investigational product within the following time period prior to the first dosing day in the current study: 30 days, 5 half lives, or twice the duration of the biological effect of the investigational product (whichever is longer).
- 16. Exposure to more than four investigational products within 12 months prior to the first dosing day.

#### Diagnostic assessments

- 17. Participants with a peripheral blood neutrophil count  $< 1.0 \times 10^9$ /L at screening
- 18. Diagnosis of pneumonia (chest X-ray or computed tomography [CT] confirmed) within the 3 months prior to screening
- 19. Chest X-ray (posterior with lateral) or CT scan reveals evidence of a clinically significant abnormality not believed to be due to the presence of COPD (historic data up to 1 year may be used).

- 20. Abnormal and clinically significant 12-lead ECG finding at screening. The investigator will determine the clinical significance of each abnormal ECG finding in relation to the participant's medical history and exclude participants who would be at undue risk by participating in the trial. An abnormal and clinically significant finding that would preclude a participant from entering the trial is defined as a 12-lead tracing that is interpreted as, but not limited to, any of the following:
  - AF with rapid ventricular rate > 120 beats per minute (bpm);
  - sustained or non-sustained ventricular tachycardia (VT)
  - second degree heart block Mobitz type II and third degree heart block (unless pacemaker or defibrillator has been implanted)
  - QT interval corrected for heart rate by Fridericia's formula (QTcF) ≥500 msec in participants with QRS <120 msec and QTcF ≥ 530 millisecond (msec) in participants with QRS ≥120 msec

#### Other Exclusions

21. Affiliation with a study site: study investigators, sub-investigators, study coordinators, employees of a study investigator, sub-investigator or study site, or immediate family members of any of the above that is involved with the study.

#### 6.3. Lifestyle Restrictions

No restrictions are required.

#### 6.3.1. Meals and Dietary Restrictions

No meal or dietary restrictions are required for participation in this study, but participants should have fasted for 6 hours prior to each visit. Danirixin must be taken with food. Specific dosing instructions will be provided in the Study Reference Manual (SRM) and will be provided to all study participants.

#### 6.3.2. Caffeine, Alcohol, and Tobacco

Participants should refrain from alcohol for 24 hours prior to each study visit, and avoid caffeine for 6 hours prior to each visit. Participants should avoid changes to their tobacco habit for the duration of the study, and, where applicable, try to refrain from smoking for 4 hours before each visit.

#### 6.3.3. Activity

Participants should abstain from strenuous exercise for 24 hours before each blood collection for clinical laboratory tests.

## 6.4. Screen Failures

Screen failures are defined as participants who consent to participate in the clinical study but are not subsequently randomized in the study. A minimal set of screen failure information is required to ensure transparent reporting of screen failure participants to meet the Consolidated Standards of Reporting Trials (CONSORT) publishing requirements and to respond to queries from regulatory authorities. Minimal information includes demography, screen failure details, eligibility criteria, and any SAEs.

Individuals who do not meet the criteria for participation in this study (screen failure) or have an exacerbation of COPD in the screening period (run-in failure) may be rescreened once. If rescreening is performed, subjects are assigned a different unique subject Identification (ID) number for the re-screening, and all the screening procedures must be repeated.

# 7. TREATMENTS

Study treatment is defined as any investigational treatment(s), marketed product(s), placebo, or medical device(s) intended to be administered to a study participant according to the study protocol.

Dosage formulation:	White Film coated tablets (oval shaped). Refer to Investigator's Brochure for presentation and excipients	White Film coated tablets (oval shaped). Refer to Investigator's Brochure for presentation and excipients
Unit dose strength(s)/Dosage level(s):	35mg HBr	N/A
Route of Administration	Oral	Oral
Dosing instructions:	One tablet to be taken twice daily with food	One tablet to be taken twice daily with food
Packaging and Labelling	Study Treatment will be provided in a High- density polyethylene (HDPE) bottle with desiccant. Each bottle will be labelled as required per country requirement.	Study Treatment will be provided in a HDPE bottle with desiccant. Each bottle will be labelled as required per country requirement.
Manufacturer	GSK	GSK

## 7.1. Treatments Administered

## 7.2. Dose Modification

No individual participant dose modifications or adjustments are allowed.

## 7.3. Method of Treatment Assignment

All participants will be centrally randomized using an Interactive Voice/Web Response System (IVRS/IWRS). Before the study is initiated, the telephone number and call-in directions for the IVRS and/or the log in information & directions for the IWRS will be provided to each site.

Study treatment will be dispensed at study visit 2 (see SoA). Returned study treatment should not be re-dispensed to the participants.

# 7.4. Blinding

The IVRS/IWRS will be programmed with blind-breaking instructions. The blind may be broken by the investigator or treating physician in the case of an emergency, or if, in the opinion of the investigator, it is in the participant's best interest for the investigator to know the study treatment assignment. The investigator is encouraged to discuss with the GSK Medical Monitor or appropriate GSK study personnel before the blind is broken. If GSK is not notified before the blind is broken, they must be notified as soon as possible after breaking the blind. The date and reason that the blind was broken must be recorded in the source documentation and electronic case report form (eCRF), as applicable.

GSK's Global Clinical Safety and Pharmacovigilance (GCSP) staff may unblind the treatment assignment for any participant with an SAE. If the SAE requires that an expedited regulatory report be sent to one or more regulatory agencies, a copy of the report, identifying the participant's treatment assignment, may be sent to investigators in accordance with local regulations and/or GSK policy.

## 7.5. Preparation/Handling/Storage/Accountability.

- 1. The investigator or designee must confirm appropriate temperature conditions have been maintained during transit for all study treatment received and any discrepancies are reported and resolved before use of the study treatment.
- 2. Only participants enrolled in the study may receive study treatment and only authorized site staff may supply or administer study treatment. All study treatments must be stored in a secure, environmentally controlled, and monitored (manual or automated) area in accordance with the labeled storage conditions with access limited to the investigator and authorized site staff.
- 3. The investigator, institution, or the head of the medical institution (where applicable) is responsible for study treatment accountability, reconciliation, and record maintenance (ie, receipt, reconciliation, and final disposition records).
- 4. Further guidance and information for the final disposition of unused study treatment are provided in the Study Reference Manual or other specified location.
- 5. Under normal conditions of handling and administration, study treatment is not expected to pose significant safety risks to site staff.

6. A Material Safety Data Sheet (MSDS)/equivalent document describing occupational hazards and recommended handling precautions either will be provided to the investigator, where this is required by local laws, or is available upon request from GSK.

#### 7.6. Treatment Compliance

- When participants are dosed at the site, they will receive study treatment directly from the investigator or designee, under medical supervision. The date and time of each dose administered in the clinic will be recorded in the source documents. The dose of study treatment and study participant identification will be confirmed at the time of dosing by a member of the study site staff other than the person administering the study treatment.
- When participants self-administer study treatment(s) at home, compliance with danirixin or placebo will be assessed through querying the participant during the site visits and documented in the source documents and case report form (CRF). A record of the number of danirixin or placebo tablets dispensed to and taken by each participant must be maintained and reconciled with study treatment and compliance records. Treatment start and stop dates will also be recorded in the CRF.

Compliance at each visit will be determined as follows:

(# dispensed - # returned) x 100 / (# days since last visit)

- Participants estimated to have taken less than 80% or more than 120% of study treatment tablets at two consecutive visits will be considered noncompliant. All attempts should be made to improve the participant's compliance in taking study treatment at visit 3.
- Treatment compliance may additionally be assessed via a digital application (a medication adherence monitoring Platform) for all participants in the study. The Platform uses artificial intelligence on smartphones to confirm treatment ingestion. In addition, built-in reminders and a communication system allow real-time intervention in case of drug interruptions. Use of this platform will in no way supersede or replace the physician and/or prescribed medication protocol of the participants. Since the platform does not change the treatment protocol of the participants, but rather encourages adherence to the study treatment to the predefined protocol, use of this platform presents minimal risk to the participants. Consenting to use of the Platform is optional for participation in the study.

The monitoring Platform requires that all participants take each dose of the study treatment while using a smartphone. The platform will be provided to participants preloaded on a smartphone, or participants can download the platform onto their own mobile device during V2.

When at home, participants will receive reminders within predefined windows to selfadminister the study treatment using the front-facing webcam on their smartphone. The application on the smartphone will make an automated determination of whether the participant has properly ingested their treatment at the prescribed time. There is no need for a healthcare provider to review the administration, nor would a healthcare provider need to be available at the time the participant takes their treatment. Further information on the Platform in available in Appendix 9.

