#### CONFIDENTIAL

Procedure	Pre-Screening and Screening 						Follow-up Phone call	Unscheduled visit 	Notes
	V0	V1	V2	V3	V 4	V5			
Dispense study medication			Х						
Monitor IP compliance (via manual counting and App)			Х	Х	Х			Digital App monitoring to begin at V2	
Collect IP					Х				

• The timing and number of planned study assessments, including safety, pharmacokinetic, pharmacodynamic/biomarker or other assessments may be altered during the course of the study based on newly available data (e.g., to obtain data closer to the time of peak plasma concentrations) to ensure appropriate monitoring.

- Any changes in the timing or addition of time points for any planned study assessments must be documented and approved by the relevant study team member and then
  archived in the sponsor and site study files, but will not constitute a protocol amendment. The IRB/IEC will be informed of any safety issues that require alteration of the safety
  monitoring scheme or amendment of the Informed consent form (ICF).
- Safety assessments should be performed in the following order where applicable/ possible: vital signs, ECG measurements, blood samples and spirometry.
  - Screening visit is split into pre-screening on visit 0 and screening on visit 1 although the visits may be performed on the same day. This is to a) enable participants to
    potentially have more than one attempt at sputum induction for meeting eligibility and b) to only collect minimal screening data for subjects who fail on the basis of the elevated
    NETs since that is the key inclusion criteria that may not be known from medical records.
  - 2. Unscheduled visits may be used to collect information related to adverse events, for follow up of any safety assessments, and also to complete assessments where participants were not able to perform these within the visit window for any reason. It is not necessary to carry out all of the assessments listed under an unscheduled visit at a single visit; the assessments performed should be driven by the need for the visit.
  - 3. VOC measurement should be undertaken prior to sputum induction at these visits.

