## 8.2. Withdrawal from the Study

- A participant may withdraw from the study at any time at his/her own request, or may be withdrawn at any time at the discretion of the investigator for safety, behavioral, compliance or administrative reasons.
- If the participant withdraws consent for disclosure of future information, the sponsor may retain and continue to use any data collected before such a withdrawal of consent.
- If a participant withdraws from the study, he/she may request destruction of any samples taken and not tested, and the investigator must document this in the site study records.

- Refer to the SoA for data to be collected at the time of study discontinuation and follow-up and for any further evaluations that need to be completed.
- Any participant who experiences a COPD exacerbation (i.e., associated with antibiotic or steroid use) will be permanently discontinued from study treatment and should return to the clinic for follow-up if possible. Only the safety assessments scheduled for the follow-up visit should be conducted in these participants as described in the SoA (Section 2).

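### The compliance formula in Protocol 7.6 leaves out the twice-daily factor, so full adherence scores 200% and half intake scores 100%

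*Protocol*

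**What the plan says.** The treatment table in Protocol Section 7 gives the dosing instruction "One tablet to be taken twice daily with food", and Section 5.1 agrees that dosing is twice daily for two weeks.

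Protocol 7.6 defines the compliance score at each visit as tablets dispensed minus tablets returned, times 100, over elapsed days: "dispensed - # returned) x 100 / (# days since last visit". The rule that follows is "Participants estimated to have taken less than 80% or more than 120% of study treatment tablets at two consecutive visits will be considered noncompliant". Sites are then asked to make every effort to improve "compliance in taking study treatment at visit 3". The same section requires sites to query the participant and keep a reconciled tablet record. It also describes a smartphone adherence platform, but "Consenting to use of the Platform is optional for participation in the study".

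On timing, Protocol 7.3 states "Study treatment will be dispensed at study visit 2 (see SoA". The Schedule of Activities has the row "Monitor IP compliance (via manual counting and App") marked at Visits 2, 3 and 4, with tablets collected at Visit 4. Visit 3 is Day 7 and Visit 4 is Day 14, each with a window of one day either side.

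SAP 12.6.2 defines compliance differently: actual doses divided by planned days times frequency, with a frequency of 2 and a planned duration of 14 days.

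**The concern.** The numerator of the protocol formula is in tablets and the denominator is in days. The result is tablets per day times 100. That is a percentage of the prescribed amount only if one tablet a day is prescribed, and here it is two. The limits of 80% and 120% are worded as shares of the study tablets, so they make sense only if full intake scores 100%.

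Followed as written, the rule inverts the classification: the adherent participant is flagged and the participant on half the tablets is not. What is at stake is the accuracy of the site compliance scores, the noncompliance flags, and one possible input to the adherence effort at Visit 3. Protocol 8.2 also says a participant "may be withdrawn at any time at the discretion of the investigator for safety, behavioral, compliance or administrative reasons". It does not cite the formula, but a wrong score could misinform that decision.

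**Working it through.** The documents report no compliance value, so there is no figure to reproduce. The check is direct arithmetic.

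**Inputs**
- Tablets per day: 2 (Protocol Section 7).
- Score as written: 100 × tablets used / days (Protocol 7.6).
- Noncompliant: below 80% or above 120% at two consecutive visits (Protocol 7.6).
- Visits: Day 1, Day 7 ± 1, Day 14 ± 1 (Schedule of Activities).
- Assumption: dosing starts on the morning of Day 1 and tablets are counted before the dose at each visit. Full adherence then uses 12 tablets by Day 7 and 26 by Day 14, that is 14 between the two visits.

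**Formula as written, tablets counted per interval, nominal visits**

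| Intake | Visit 3 (6 days) | Visit 4 (7 days) | Classification |
|---|---|---|---|
| Full | 100 × 12/6 = 200% | 100 × 14/7 = 200% | Noncompliant |
| Half | 100 × 6/6 = 100% | 100 × 7/7 = 100% | Compliant |

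Full intake scores 200, so the limits translate to 80/200 = 40% and 120/200 = 60% of the prescribed tablets. In whole tablets, the passing band is 5 to 7 of 12 at Visit 3 and 6 to 8 of 14 at Visit 4.

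**Visit windows and count timing.** With Visit 3 on Days 6 to 8 and Visit 4 on Days 13 to 15, an interval lasts n = 5 to 9 days. Full adherence gives 100 × 2n/n = 200% for every n. Allow one tablet either way for count timing:
- Full adherence: 100 × (2n ± 1)/n, widest at n = 5, which is 180% to 220%. This is always above 120%.
- Half intake: 100 × (n ± 1)/n, widest at n = 5, which is 80% to 120%. This is never outside the limits, because the rule flags only values below 80% or above 120%.

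**Cumulative reading at Visit 4.** Tablets are dispensed once, at Visit 2, and 7.6 does not say that the Visit 4 count starts from the Visit 3 count. If a site divides all tablets used since Visit 2 by the days since Visit 3:
- As written: full 100 × 26/7 = 371%, half 100 × 13/7 = 186%. The two-visit classification is unchanged, because half intake still scores 100% at Visit 3.
- With only the factor 2 added: full 100 × 26/14 = 186% and half 100 × 13/14 = 93% at Visit 4, after 100% and 50% at Visit 3. Neither is out of range at two consecutive visits, so half intake still escapes the flag.

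**Corrected formula, 100 × interval tablets / (2 × interval days)**
- Full: 100 × 12/12 = 100% and 100 × 14/14 = 100%.
- Half: 100 × 6/12 = 50% and 100 × 7/14 = 50%, flagged.
- Full with the one-tablet difference: 100 × (2n ± 1)/(2n), widest at n = 5, which is 90% to 110%, inside the limits.

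**Against the SAP.** Over the whole study SAP 12.6.2 gives 28/(14 × 2) = 100% for full intake and 14/(14 × 2) = 50% for half. The corrected protocol formula agrees with this; the current one does not.

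**The case against.** The arithmetic is not in dispute, but there is a fair case that little follows from it.

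- **The flag comes late.** It needs two consecutive visits, and only Visits 3 and 4 fall after dosing starts. It can first arise at Visit 4, when the tablets are handed back, so it cannot drive withdrawal from treatment. This stands: only the Visit 3 score could reach a decision under Protocol 8.2.
- **The rule does not name the formula.** It speaks of tablets estimated to have been taken. A site working straight from the reconciled tablet record would put a fully adherent participant at 100%. This stands in part. The formula directly precedes the rule and is given as the way compliance will be determined, so using it is the natural reading. The misclassification is nevertheless conditional on the score being used.
- **The Visit 3 adherence effort is not tied to a score.** This stands; the score is at most one input.
- **Reporting is already right.** The SAP uses the frequency of 2, no population in SAP Section 4 depends on compliance, and SAP 12.1.1 defines no per-protocol analysis. This stands and sets the severity.
- **Nothing shows that a flag was recorded this way, and the study has stopped.** This stands, so the recheck is conditional.

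None of this makes the formula correct. The optional platform does not replace the tablet count for every participant.

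**Conclusion.** The concern holds. As written, Protocol 7.6 doubles the score of every participant relative to the prescribed tablets, and its limits accept 40% to 60% intake. On an interval count, full adherence scores 200% and half intake 100% whatever the interval length. A one-tablet counting difference within the permitted windows does not change either classification. The exact tablet counts rest on a morning start on Day 1 and a pre-dose count; the factor of two does not.

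The severity is minor. The error reaches site scores and flags, and possibly a discretionary decision informed by the Visit 3 score. It does not reach SAP-derived compliance, the analysis populations or the primary estimate.

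**What to change.** Change the Protocol 7.6 formula to tablets used in the interval × 100 / (2 × days in that same interval), and leave the stated 80% and 120% limits as they are. State that the Visit 4 count runs from the Visit 3 count. Alternatively, use cumulative tablets over cumulative days since Visit 2 at both visits, which gives 100 × 26/(2 × 13) = 100% for full adherence at Visit 4. The interval must be stated because the factor 2 alone does not repair a mixed count. Cross-refer to SAP 12.6.2 so that both documents use the same frequency.

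The cost is a one-line clarification or a file note. SAP 3.2 records that the study stopped early with 19 completers, so the useful action is to recheck any noncompliance flag or deviation that rested on the formula, and to look for low intake that it missed. The tablet records that 7.6 already requires are enough; no new data are needed.
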